2. INTRODUCTION

This SAP provides the detailed methodology for summary and statistical analyses of the data collected in Study C4781001 – Substudy B. This document may modify the plans outlined in the protocol; however, any major modifications of the primary endpoint definition or its analysis will also be reflected in a protocol amendment.

2.1. Modifications to the Analysis Plan Described in the Protocol

The following modifications were made: added 240 participants from 18 through 64 years of age, who will receive either 1 dose of CCI qIRV or 1 dose of CCI qIRV; added the primary safety, secondary, and tertiary objectives of immune responses elicited by qIRV in adults from 18 through 64 years of age and their corresponding estimands and endpoints; and removed the tertiary estimands and endpoints for all the heterologous strains.

2.2. Study Objectives, Endpoints, and Estimands Substudy B (Phase 1/2)

[figure not shown]
Туре	Objectives	Estimands	Endpoints
Primary safety	To describe the safety and tolerability of modRNA influenza vaccines when administered in differing vaccination schedules in adults 18 to 64 and 65 to 85 years of age	In participants receiving at least 1 dose of study intervention, the percentage of participants reporting: • Local reactions for up to 7 days following each vaccination • Systemic events for up to 7 days following each vaccination • AEs from the first vaccination to 4 weeks after the last vaccination • SAEs from the first vaccination to 6 months after the last vaccination The percentage of participants with: • Abnormal troponin I laboratory values 2 days after the last vaccination The percentage of participants with: • New ECG abnormalities 2 days after the last vaccination	Local reactions (pain at the injection site, redness, and swelling) Systemic events (fever, fatigue, headache, chills, vomiting, diarrhea, new or worsened muscle pain, and new or worsened joint pain) AEs SAEs Troponin I laboratory parameters ECG abnormalities consistent with probable or possible myocarditis or pericarditis
Secondary immune responses	To describe the immune responses elicited by modRNA influenza vaccines when administered in differing vaccination schedules in adults 65 to 85 years of age	 In participants complying with the key protocol criteria (evaluable participants) at Day 21 (if applicable) and 1, 4, and 8 weeks after receipt of the last vaccination: HAI GMTs before Vaccination 1, prior to Vaccination 2 (Day 21, if applicable), and at 1, 4, and 8 weeks after receipt of the last vaccination HAI GMFR from before Vaccination 1 to prior to Vaccination 2 (Day 21, if applicable) and to 1, 4, and 8 weeks after receipt of the last vaccination The proportion of participants achieving HAI seroconversion for each strain prior to Vaccination 2 (Day 21, if applicable) and at 1, 4, and 8 weeks after receipt of the last vaccination The proportion of participants with HAI titers ≥1:40 for each strain before Vaccinations 1 and 2 (Day 21, if applicable) and at 1, 4, and 8 weeks after receipt of the last vaccination 	HAI titers for each strain targeted by the study vaccine

$Protocol\,C4781001-Substudy\,B\,(PF-07252220)\,Statistical\,Analysis\,Plan$

Туре	Objectives	Estimands	Endpoints
		In participants who have received at least 1 dose of a quadrivalent vaccine, complying with the key protocol criteria (evaluable participants), at Day 21 (if applicable) and at 1, 4, and 8 weeks after receipt of the last vaccination: • The proportion of participants achieving HAI seroconversion for all strains prior to Vaccination 2 (Day 21, if applicable) and at 1, 4, and 8 weeks after receipt of the last vaccination • The proportion of participants with HAI titers ≥1:40 for all strains before Vaccinations 1 and 2 (Day 21, if applicable) and 1, 4, and 8 weeks after receipt of the last vaccination	HAI titers for each strain targeted by the study vaccine
	To describe the immune responses elicited by qIRV in adults 18 to 64 years of age	 In participants complying with the key protocol criteria (evaluable participants) at 1, 4, and 8 weeks after receipt of vaccination: HAI GMTs before vaccination and at 1, 4, and 8 weeks after receipt of vaccination HAI GMFR from before vaccination to 1, 4, and 8 weeks after receipt of vaccination The proportion of participants achieving HAI seroconversion for each strain at 1, 4, and 8 weeks after receipt of vaccination The proportion of participants with HAI titers ≥1:40 for each strain before vaccination and at 1, 4, and 8 weeks after receipt of vaccination The proportion of participants achieving HAI seroconversion for all strains at 1, 4, and 8 weeks after receipt of vaccination The proportion of participants with HAI titers ≥1:40 for all strains before vaccination and 1, 4, and 8 weeks after receipt of vaccination 	HAI titers for each strain targeted by the study vaccine

2.2.1. Primary Safety Estimands

The primary estimands for the primary objective will follow the treatment policy strategy from the EMA ICH E9 (R1) addendum¹ and estimate the safety percentages regardless of the occurrence of intercurrent event(s) or rescue medication use. The analyses will be based on the actual vaccine received.

In participants receiving at least 1 dose of study intervention:

• The percentage of participants reporting prompted local reactions up to 7 days following each vaccination.

This estimand includes the following attributes:

- Treatment: 1-Visit schedules or 2-visit schedules with modRNA, licensed QIV, and/or placebo or their combinations as listed in Table 2.
- Population: Safety population for 1-visit schedules and Vaccination 1 safety population or Vaccination 2 safety population for 2-visit schedules as defined in Section 4.
- Variable: Presence/absence of prespecified local reactions up to 7 days after each vaccination.
- Intercurrent event(s): For participants who discontinue receipt of study intervention or discontinue participation in the study.
- Population-level summary: Percentage and associated 2-sided 95% CI of participants reporting local reactions in each vaccine group.
- The percentage of participants reporting prompted systemic events up to 7 days following each vaccination.

- Treatment: 1-Visit schedules or 2-visit schedules with modRNA, licensed QIV, and/or placebo or their combinations as listed in Table 2.
- Population: Safety population for 1-visit schedules and Vaccination 1 safety population or Vaccination 2 safety population for 2-visit schedules as defined in Section 4.
- Variable: Presence/absence of prespecified systemic events up to 7 days after each vaccination.
- Intercurrent event(s): Participants discontinue.

- Population-level summary: Percentage and associated 2-sided 95% CI of participants reporting systemic events in each vaccine group.
- The percentage of participants reporting AEs from the first vaccination to 4 weeks after the last vaccination.

This estimand includes the following attributes:

- Treatment: 1-Visit schedules or 2-visit schedules with modRNA, licensed QIV, and/or placebo or their combinations as listed in Table 2.
- Population: Safety population as defined in Section 4.
- Variable: Presence of AEs from the first vaccination to 4 weeks after the last vaccination.
- Intercurrent event(s): Participants discontinue.
- Population-level summary: Percentage and associated 2-sided 95% CI of participants reporting AEs from the first vaccination to 4 weeks after the last vaccination in each vaccine group.
- The percentage of participants reporting SAEs from the first vaccination to 6 months after the last vaccination.

- Treatment: 1-Visit schedules or 2-visit schedules with modRNA, licensed QIV, and/or placebo or their combinations as listed in Table 2.
- Population: Safety population as defined in Section 4.
- Variable: Presence of SAEs from the first vaccination to 6 months after the last vaccination.
- Intercurrent event(s): Participants discontinue.
- Population-level summary: Percentage and associated 2-sided 95% CI of participants reporting SAEs from the first vaccination to 6 months after the last vaccination in each vaccine group.
- The percentage of participants with abnormal troponin I laboratory values 2 days after the last vaccination.

This estimand includes the following attributes:

- Treatment: 1-Visit schedules or 2-visit schedules with modRNA, licensed QIV, and/or placebo or their combinations as listed in Table 2.
- Population: Safety population for 1-visit schedules and Vaccination 1 safety population or Vaccination 2 safety population for 2-visit schedules as defined in Section 4.
- Variable: Presence of abnormal troponin I laboratory values 2 days after the last vaccination. A troponin I value >0.3 μg/L is considered abnormal as per the reference range of the contracted vendor laboratory.
- Intercurrent event(s): Participants discontinue.
- Population-level summary: Percentage and associated 2-sided 95% CI of participants with abnormal troponin I laboratory values 2 days after the last vaccination in each vaccine group.
- The percentage of participants with new ECG abnormalities 2 days after the last vaccination.

This estimand includes the following attributes:

- Treatment: 1-Visit schedules or 2-visit schedules with modRNA, licensed QIV, and/or placebo or their combinations as listed in Table 2.
- Population: Safety population for 1-visit schedules and Vaccination 1 safety population or Vaccination 2 safety population for 2-visit schedules as defined in Section 4.
- Variable: Presence of new ECG abnormalities (as defined in Section 3.1.1.7) 2 days after the last vaccination.
- Intercurrent event(s): Participants discontinue.
- Population-level summary: Percentage and associated 2-sided 95% CI of participants with new ECG abnormalities 2 days after the last vaccination in each vaccine group.

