13. Participation in other studies involving study intervention within 28 days prior to study entry and/or during study participation.	X

	Substudy B
Other Exclusions:	
14. Investigator site staff or Pfizer employees directly involved in the conduct of the study, site staff otherwise supervised by the investigator, and their respective family members.	X
15. Participation in strenuous or endurance exercise through Visit 205.	X
16. Prior history of heart disease.	X
17. Any abnormal screening troponin I laboratory value.	X
18. Screening 12-lead ECG that, as judged by the investigator, is consistent with probable or possible myocarditis or pericarditis, or demonstrates clinically relevant abnormalities that may affect participant safety or interpretation of study results. Participants with a screening 12-lead ECG that shows an average QTcF interval >450 msec, complete left bundle branch block, signs of an acute or indeterminate-age myocardial infarction, ST-T interval changes suggestive of myocardial ischemia, second- or third-degree AV block, or serious bradyarrhythmias or tachyarrhythmias should be excluded from study participation.	X

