10.10.8.8. Substudy B Procedures

10.10.8.8.1. Screening (0 to 28 Days Before Visit 201)

Before enrollment and before any study-related procedures are performed, voluntary, written, study-specific informed consent will be obtained from the participant. Each signature on the ICD must be personally dated by the signatory. The investigator or his or her designee will also sign the ICD. A copy of the signed and dated ICD must be given to the participant. The source data must reflect that the informed consent was obtained before participation in the study.

It is anticipated that the procedures below will be conducted in a stepwise manner.

- Assign a single participant number using the IRT system.
- Obtain the participant's demography (including date of birth, sex, race, and ethnicity). The full date of birth will be collected to critically evaluate the immune response and safety profile by age.
- Obtain any medical history of clinical significance.
- Obtain details of any medications currently taken.
- Perform 12-lead triplicate ECG.
- Perform physical examination, including vital signs (weight, height, body temperature, pulse rate, and seated blood pressure), evaluating any clinically significant abnormalities within the following body systems: general appearance; skin; head, eyes, ears, nose, and throat; heart; lungs; abdomen; musculoskeletal; extremities; neurological; and lymph nodes.
- Collect a blood sample of approximately 2.5 mL as detailed in the laboratory manual for troponin I laboratory testing as described in Section 10.2.
- Perform urine pregnancy test on WOCBP as described in Section 8.2.5.
- Discuss contraceptive use as described in Section 10.4.
- Record nonstudy vaccinations as described in Section 6.8.
- Record prior receipt of any COVID-19 vaccine as described in Section 6.8.
- Record details of any licensed influenza vaccine received in the prior 12 months, as described in Section 6.8.
- Ensure and document that all of the inclusion criteria and none of the exclusion criteria are met.

- Record AEs as described in Section 8.3.
- Remind the participant to use appropriate contraceptives throughout the study, if applicable.
- The investigator or an authorized designee completes the CRF.

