10.10.8.8.2. Visit 201 – Vaccination 1 (Day 1)

It is anticipated that the procedures below will be conducted in a stepwise manner; ensure that procedures listed prior to administration of the vaccine are conducted prior to vaccination.

- Discuss contraceptive use as described in Section 10.4.
- Record nonstudy vaccinations as described in Section 6.8.
- Review screening laboratory troponin I and ECG results.
- Perform a clinical assessment. If the clinical assessment indicates that a physical examination is necessary to comprehensively evaluate the participant, perform a physical examination and record any findings in the source documents and, if clinically significant, record on the medical history CRF.
- Perform 12-lead triplicate ECG.
- Collect a blood sample of approximately 2.5 mL as detailed in the laboratory manual for troponin I laboratory testing as described in Section 10.2.
- Measure vital signs, including body temperature, pulse rate, and seated blood pressure.
- Perform urine pregnancy test on WOCBP as described in Section 8.2.5.
- Ensure that the participant continues to meet all of the inclusion criteria and none of the exclusion criteria.
- Ensure that the participant meets none of the temporary delay criteria as described in Section 5.5.
- Obtain the participant's randomization number and study intervention allocation using the IRT system.
- Collect a blood sample (approximately 50 mL), before administration of study intervention, for immunogenicity assessment.

- If the participant has consented to provide a blood sample for description of cell-mediated immune response, collect a blood sample (approximately 50 mL) for PBMC isolation.
- Site staff member(s) will dispense/administer study intervention, depending on the allocated study intervention/vaccine schedule, as detailed in Table 6. Please refer to the IP manual for further instruction on this process.
- Site staff must observe the participant for at least 30 minutes after study intervention administration for any acute reactions. Record any acute reactions (including time of onset) in the participant's source documents and on the AE page of the CRF, and on an SAE form as applicable.
- Issue a measuring device to measure local reactions at the injection site and a thermometer for recording daily temperatures and provide instructions on their use.

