3.1.1.6. Chemistry Laboratory Parameters

Troponin I laboratory parameters will be collected. The primary endpoints include abnormal troponin values 2 days after the last vaccination.

The troponin I tests will be performed at screening and Visits 201 (Day 1) and 204 (2 to 4 days after the last vaccination).

The investigator must review the laboratory report, document this review, and record any clinically relevant changes occurring during the study in the AE section of the CRF.

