6.1.1.5. Chemistry Laboratory Parameters

6.1.1.5.1. Abnormal Troponin I Laboratory Values

6.1.1.5.1.1. Main Analysis

- Estimand: The percentage of participants with abnormal troponin I values 2 days after the last vaccination.
- Estimand strategy: Treatment policy (Section 2.2.1).
- Analysis set: Safety population for 1-visit schedules and Vaccination 1 safety population or Vaccination 2 safety population for 2-visit schedules (Section 4).
- Analysis time point: 2 Days after the last vaccination.
- Analysis methodology: Descriptive summary statistics.
- Intercurrent events and missing data: For participants who discontinue, all collected data will be included; missing abnormal test values will be handled according to Pfizer safety rules.
- Reporting results: The number of participants with abnormal troponin I values 2 days after the last vaccination (n), proportion, and associated 2-sided Clopper-Pearson 95% CI will be presented for each test by vaccine group.

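### The Substudy B troponin I endpoint makes no use of the Day 1 pre-vaccination sample, so an elevation that arises between screening and Day 1 can be reported as a post-vaccination abnormality; add a baseline-referenced summary beside it.

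*SAP*

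**What the plan says.** The endpoint appears in SAP 2.2.1, 3.1.1.6 and 6.1.1.5 and in protocol 10.10.3 and 10.10.9.3.2.

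- **Variable (SAP 2.2.1):** "Variable: Presence of abnormal troponin I laboratory values 2 days after the last vaccination". The cut-off is absolute: "A troponin I value >0.3 μg/L is considered abnormal as per the reference range of the contracted vendor laboratory".
- **Sampling (SAP 3.1.1.6):** "The troponin I tests will be performed at screening and Visits 201 (Day 1) and 204 (2 to 4 days after the last vaccination").
- **Analysis (SAP 6.1.1.5.1):** "Estimand: The percentage of participants with abnormal troponin I values 2 days after the last vaccination". The output is a count, a proportion and a Clopper-Pearson interval by vaccine group. No shift or change from Day 1 is planned.
- **Eligibility (protocol 10.10.5.2, criterion 17):** the exclusion is "Any abnormal screening troponin I laboratory value". Screening falls 0 to 28 days before Visit 201 (protocol 10.10.8.8.1).
- **Visit 201 (protocol 10.10.8.8.2):** the troponin review listed before dosing is "Review screening laboratory troponin I and ECG results". A fresh sample is then drawn, and it precedes the dose because sites must "ensure that procedures listed prior to administration of the vaccine are conducted prior to vaccination". No step calls for the fresh result before dose 1.

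SAP 3.4 treats pre-vaccination samples as baseline in general terms, but the troponin estimand and analysis do not draw on that.

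**The concern.** Troponin I is a primary safety measure, reported alongside an ECG endpoint aimed at possible myocarditis or pericarditis. A reader will take the percentage as something that followed vaccination. As defined, it mixes two kinds of participant: those who became abnormal after vaccination, and those who were already abnormal in the Day 1 sample. The planned table cannot tell them apart, although the data to do so are collected.

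The plan applies a different standard elsewhere. The adjacent ECG estimand counts only *new* abnormalities. Substudy A, whose chemistry panel includes troponin I, has a grading-shift estimand in addition to its abnormal-value estimand. Substudy B has no counterpart for troponin.

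With groups of 15 or 120 and few events likely, a single misattributed case changes what a group's row says.

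**Working it through.** **1. Can the case arise?** For a 1-visit schedule:

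- Screening value normal, so criterion 17 is passed, up to 28 days before Visit 201.
- Visit 201: screening result reviewed, new sample drawn, vaccine given.
- In the Substudy B schedule of activities, the next troponin review that applies to a 1-visit schedule is at Visit 205. Visits 202 and 203 are for 2-visit schedules only.
- Visit 204, the endpoint sample, comes before Visit 205.

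A value above 0.3 μg/L at both Visit 201 and Visit 204 is therefore counted, and no planned output shows that it was there before the dose.

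For 2-visit schedules, Visit 204 falls 19 + 2 = 21 to 23 + 4 = 27 days after Day 1. The elevation would have to last that long. Troponin results are also reviewed at Visit 202 (initial enrollment) and at Visit 203, before dose 2.

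**2. The plan's own figure.** Protocol Table 4 gives the probability of at least one event as 0.70 for N = 120 and a true rate of 1.0%. With P = 1 − (1 − p)^N, 1 − 0.99^120 = 0.701, which agrees. The same formula is used in step 4.

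**3. Effect of one carried-over case.** The group sizes are 15 (initial) and 120 (expanded), from protocol 9.5. SAP 5.2 analyzes the two stages separately, so these are the right denominators. The intervals are Clopper-Pearson:

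- 0 events: upper limit 1 − 0.025^(1/N).
- 1 event: lower limit 1 − 0.975^(1/N); upper limit is the 0.975 quantile of Beta(2, N − 1).

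| Group size | No case | One carried-over case |
|---|---|---|
| 15 | 0% (0 to 21.8) | 6.7% (0.2 to 31.9) |
| 120 | 0% (0 to 3.03) | 0.83% (0.02 to 4.56) |

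**4. How often?** Two quantities are needed: q, the rate of an abnormal Day 1 value after a normal screen, and r, the fraction of these still abnormal at Visit 204. The documents give neither. The values below are assumptions.

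Expected cases in 120 = 120 × q × r. P(at least one) = 1 − (1 − q × r)^N.

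| q | r | Expected per 120 | P, N = 15 | P, N = 120 |
|---|---|---|---|---|
| 0.1% | 50% | 0.06 | 0.007 | 0.06 |
| 0.1% | 100% | 0.12 | 0.015 | 0.11 |
| 0.5% | 50% | 0.3 | 0.04 | 0.26 |
| 0.5% | 100% | 0.6 | 0.07 | 0.45 |
| 1% | 50% | 0.6 | 0.07 | 0.45 |
| 1% | 100% | 1.2 | 0.14 | 0.70 |
| 2% | 50% | 1.2 | 0.14 | 0.70 |
| 2% | 100% | 2.4 | 0.26 | 0.91 |

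The range runs from practically nothing to more than two cases per group of 120. The documents cannot narrow it.

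**The case against.** The case for leaving the plan alone has real weight.

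- **The pool is small.** Criterion 17 removes elevations present at screening and criterion 16 removes prior heart disease, so stable chronic elevations are largely kept out. What is left is a value that turns abnormal within at most 28 days and persists to Visit 204. This stands, and it is why the low end of the range matters.
- **The analysis is descriptive and safety decisions do not run on it.** Substudy B has no hypotheses. The troponin stopping criterion in protocol 10.10.8.6 needs confirmation by a repeat test and an investigator's judgment of relatedness. This stands.
- **Control groups carry the same background.** In participants aged 65 to 85, licensed QIV groups are measured in the same way, and SAP 5.2.1.1 plans between-group intervals. This stands in part. Both groups aged 18 to 64 receive qIRV with no QIV comparator, and the older groups may not all be randomized concurrently.
- **Substudy A also reports an absolute abnormal-value endpoint.** This is correct. Its shifts are an extra estimand, not a replacement. It argues for adding a shift summary here, not for redefining the endpoint.
- **A purely *new* endpoint would lose information.** It would not count someone slightly abnormal on Day 1 who rises sharply after the dose, and it would drop vaccinated participants without a Day 1 result. This stands, and the fix allows for it.

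A reader might also infer that participants with no Visit 204 sample are counted as non-events. The documents do not settle this: SAP 5.3.1 and 6.1.1.5 refer missing laboratory values to the sponsor's safety rules, which are not included.

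**Conclusion.** The gap is real but narrow. The Substudy B troponin endpoint has no baseline condition, the Day 1 sample that would supply one is unused, and one path (normal at screening, abnormal on Day 1, still abnormal at Visit 204) leads to a pre-vaccination elevation being reported as a post-vaccination abnormality. One such case moves a group from 0% to 6.7% (N = 15) or 0.8% (N = 120). At assumed carried-over rates of 0.1% to 2%, the chance of at least one in 120 is 0.11 to 0.91; these rates are not document figures.

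Three stronger readings are tempting and not supported. The endpoint does not count abnormal values at any later time; it is the single Visit 204 sample. The documents do not show that pre-existing elevations would make up most of the reported percentage, or that the right answer in any group is zero, since no background rate is given. Nor does the point affect pausing of the trial. What remains is an interpretability problem in a primary descriptive percentage, which data already collected can resolve.

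**What to change.** Keep the current percentage as the primary result. Add to SAP 6.1.1.5, by vaccine group:

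- a Visit 201 by Visit 204 troponin I shift table (not abnormal, abnormal, missing at each visit), so that participants abnormal on Day 1 and those with missing results stay visible;
- the number, proportion and Clopper-Pearson 95% CI of participants with new abnormal troponin I (not abnormal at Visit 201, abnormal at Visit 204) among those with both results.

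State that Visit 201, not screening, is the baseline for this summary. Add a note that in 2-visit schedules no troponin is scheduled between Day 1 and Visit 204, so this baseline cannot separate dose 1 from dose 2.

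The cost is a few lines of SAP text and two added summaries. There are no extra samples or visits and no change to dosing or stopping procedures. Because the primary endpoint definition stays as it is, the requirement in protocol section 9 and SAP section 2 to reflect major endpoint changes in a protocol amendment should not be triggered.
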